**10.2 KEY SECONDARY EFFICACY MEASURES**

The effect of treatment will be formally tested on the following 3 secondary endpoints:

- Change from Baseline in 6MWD at Week 24
- Change from Baseline in NT-proBNP at Week 24
- Change from Baseline in combined 6MWD/Borg dyspnea score at Week 24

The tests for these 3 key secondary efficacy endpoints will be hierarchical with a fixed sequence approach as described in Section 8.4.

**10.2.1 Analysis of 6MWD Including Change from Baseline to Week 24**

The efficacy endpoint of 6MWD assesses if UT-15C increases the distance traversed in the 6MWT at Week 24 over placebo in subjects with PAH. The null and alternative hypotheses are:

$$H_0: \mu_1 = \mu_2$$

$$H_a: \mu_1 \neq \mu_2$$

where  $\mu_1$  and  $\mu_2$  are the mean change from Baseline in 6MWD of the UT-15C and placebo treatment groups, respectively.

A longitudinal data analysis using mixed model repeated measurement (MMRM) will be performed to estimate the treatment difference in change in 6MWD at Week 24. The MMRM model will be based on the observed measures up to Week 24 and will include the changes from Baseline in 6MWD as the dependent variable; treatment, week, treatment by week interaction, and background PAH therapy as fixed effects; and Baseline 6MWD as a covariate. An unstructured variance/covariance structure shared across treatment groups will be used to model the within-subject errors and Kenward-Roger method will be used for calculating the denominator degree of freedom. The appropriate contrasts will be constructed in order to estimate treatment effect at Week 24 and other visits. The pseudo SAS codes are as following:

```
proc mixed;
  class trt01p(ref='PLACEBO') BGTX avisitn usubjid;
  model DistC = trt01p BGTX avisitn trt01p*avisitn
```

```

          Dist0/ddfm = kr;
repeated avisitn /type= un subject = usubjid;
lsmeans trt01p*avisitn/diff;
estimate "at Week 24" trt01p 1 -1
          trt01p*avisitn    0 0 0 1
          0 0 0 -1/cl;

run;

```

where BGTX is background PAH therapy, DistC is the change from Baseline in 6MWD, and Dist0 is the Baseline measure of the 6MWD.

From the same model, the contrasts will also be constructed to estimate the treatment effects at Weeks 4, 8, 12 assessments.

All 6MWT data will be listed for all subjects. For each scheduled assessment, this listing will include the date test was performed (or date test was intended to be performed if subject is unable to attempt the test), start time of the test, nominal time point, total distance walked (in meters), Borg dyspnea score, whether subject received oxygen during the test, and any circumstances that adversely affected the walk (if any), including reason for not attempting test (if any).

For each visit (Week 24 for key secondary efficacy endpoint, and other visits for exploratory efficacy endpoints), the effect of UT-15C versus placebo on 6MWD will also be evaluated using non-parametric analysis of covariance within the framework of the extended Cochran-Mantel-Haenszel test (Koch 1990, Koch 1998, Stokes 2000). Specifically, a Cochran-Mantel-Haenszel mean score test will be used on the standardized mid-ranks (ie, overall rank divided by the number of ranks +1, or “modified ridit” scores) of the residuals from an ordinary least squares regression with change from Baseline in 6MWD at Week 24 as a linear function of background therapy (as a categorical variable: PDE5-I/sGC stimulator or ERA) and distance walked at Baseline (as a continuous variable). This methodology will be carried out as follows:

1. Walk distances obtained subsequent to study drug termination or unblinding will be excluded (as described in Section 8).
2. Calculating ranks by background PAH therapy subgroup. The pseudo SAS codes are as following:

```
proc rank nplus1 ties=mean out=ranks;
  by BGTX;
  var DistC Dist0;
run;
```

where BGTX is background PAH therapy, DistC is the change from Baseline in 6MWD, and Dist0 is the Baseline measure of the 6MWD.

3. Separate linear regression models for each background PAH therapy group will be fit using the rank values generated above. The pseudo SAS codes are as following:

```
proc reg data=ranks noprint;
  by BGTX;
  model DistC=Dist0;
  output out=residual r=resid;
run;
```

where BGTX is background PAH therapy, DistC is the rank value of the change from Baseline in 6MWD, and Dist0 is the rank value of the Baseline measure of the 6MWD.

4. A stratified mean score test, using the values of the residuals as scores, compares the treatment groups. Cochran-Mantel-Haenszel mean score statistic and p-value will be calculated using the NOPRINT and CMH2 options in the TABLES statement of the FREQ procedure of SAS. The actual stratification used to randomize each subject will be used. The pseudo SAS codes are as following:

```
proc freq;
  tables BGTX*treatment*resid / noprint cmh2;
run;
```

where BGTX is background PAH therapy, Treatment indicates the randomized treatment group, and Resid is the residuals obtained from the above linear regression models.

In addition to the p-value from the non-parametric analyses of covariance described above, the Wilcoxon rank sum test and the Hodges-Lehmann estimate of median difference (as an estimate of location shift between 2 treatment groups for the placebo-controlled treatment effect) will be provided. The Wilcoxon rank sum test and the Hodges-Lehmann estimate can be obtained through the following pseudo SAS codes:

```
proc npar1way hl Wilcoxon;
  class treatment;
  var DistC;
run;
```

where DistC is the change from Baseline in 6MWD at a specific visit.

The least square mean, least square mean difference, and p-value for treatment group comparison will also be provided using the parametric method — analysis of covariance model where the change from Baseline in 6MWD is the dependent variable, treatment and background PAH therapy are fixed effects, and Baseline 6MWD is a covariate.

#### ***10.2.1.1 Sensitivity and Sub-group Analyses***

This methodology for key secondary efficacy analysis of change in 6MWD at Week 24 using MMRM will also be carried out with data up to Week 48 included in the model. The treatment effects at weeks 36 and 48 will be estimated.

With non-parametric analysis of covariance method, in order to analyze walk distances at each scheduled assessment, values for missing or excluded assessments up to Week 48 will be imputed according to rules described under “Missing data handling for 6MWD” in Section 8.3. Missing values beyond Week 48 will not be imputed. The visits beyond Week 48 will only be summarized using the observed values.

To further support the robustness and assess the sensitivity of efficacy analysis of change in 6MWD at Week 24, the above MMRM method will be repeated using each of the following modifications:

- MMRM model with the Per-Protocol Population
- MMRM model with only subjects achieve total daily dose  $\geq 9$  mg.

Analyses using non-parametric analysis of covariance will be repeated using each of the following modifications (as data permit):

- With the Per-Protocol Population
- Using only the observed values without imputation
- Including data collected after termination of the study drug
- Analyses will be carried out within PAH etiology categories
- Analyses will be carried out within Baseline WHO FC categories
- Analyses will be carried out within PAH background therapy categories
- Analyses will be carried out within Baseline 6MWD categories ( $\leq 350$  meters versus  $> 350$  meters)

- Analyses will be carried out within geographic regions
- Analyses will be carried out within sex
- Analyses will be carried out within age group (<65 years versus ≥65 years)
- Analyses will be carried out by study drug dose at Week 24 (total daily dose <9 mg and ≥9 mg)
- Analyses will be carried out within UT-15C dose quartile at Week 24
- Plot of 6MWD at Week 24 by UT-15C dose

### 10.2.2 *NT-proBNP*

The efficacy endpoint of NT-proBNP assesses if UT-15C decreases the level of NT-proBNP at Week 24 over placebo in subjects with PAH. The null and alternative hypotheses are:

$$H_0: \mu_1 = \mu_2$$

$$H_a: \mu_1 \neq \mu_2$$

Where  $\mu_1$  and  $\mu_2$  are the mean change from Baseline for log-transformed data in NT-proBNP of the UT-15C and placebo treatment groups, respectively, and the change from Baseline is calculated as  $\log(\text{value at week 24}) - \log(\text{value at Baseline})$ .

The NT-proBNP values will be listed for all subjects. The values and their respective changes from Baseline will be summarized for each assessment. The summary will also include the geometric mean and geometric standard deviation. The difference between treatment groups for the change from Baseline for log-transformed data at each assessment at Week 24 will be tested using an analysis of covariance model with change from Baseline for log-transformed data in NT-proBNP as the dependent variable, treatment as a fixed effect, and Baseline NT-proBNP as a covariate. The pseudo SAS codes are as following:

```
proc mixed;
  class treatment;
  model BNP_C=Treatment BNP_B;
run;
```

where BNP\_C is the change from Baseline for log-transformed data in NT-proBNP at a specific visit and BNP\_B is the NT-proBNP for log-transformed data at Baseline.

Subjects who do not have a valid NT-proBNP measurement at Baseline or Week 24 will be excluded from the analysis. Additional analyses will also be performed for the data with imputation where for subjects who do not have NT-proBNP measurements at Week 24, the LOCF imputation will be used.

A longitudinal data analysis using MMRM will also be performed to estimate the treatment difference in changes from Baseline for log-transformed data in NT-proBNP at Week 24. The MMRM will include the change from Baseline for log-transformed data in NT-proBNP as the dependent variable; treatment, week, and treatment by week interaction as fixed effects; and Baseline NT-proBNP for log-transformed data as a covariate. An unstructured variance/covariance structure shared across treatment groups will be used to model the within-subject errors and Kenward-Roger method will be used for calculating the denominator degree of freedom. The appropriate contrasts will be constructed in order to estimate treatment effect at Week 24 and other visits.

NT-proBNP data in observed cases will be descriptively summarized for other visits with measurements.

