### 8.3 PREMATURE DISCONTINUATION AND MISSING DATA

Clinical worsening events are evaluated up to the end of the study. In this event-driven study, at the end of the study, some subjects will not have clinical worsening events; some will discontinue the study early or be lost-to-follow-up before experiencing a clinical worsening event. For the time to clinical worsening event data, a censoring algorithm will be employed.

The 6MWD and other secondary efficacy endpoints are evaluated up to the end of the study; however, the analyses are mainly focused on the data up to Week 48. For 6MWD and other key secondary efficacy endpoints, missing data will be imputed as described in the sections below.

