### ***8.3.3 Missing Data Handling for Other Efficacy Assessments***

Similar to 6MWD, analogous rules will be used for the main analyses of Borg dyspnea score and WHO FC. For subjects whose Borg dyspnea score or WHO FC at visits up to Week 48 or NT-proBNP values up to Week 36 are missing, the value will be imputed as follows:

Borg dyspnea score:

- For those subjects who withdrew early due to death, are too ill to perform 6MWT, or have no Borg dyspnea score due to clinical worsening event, the Borg dyspnea score is set to the worst score of 10.
- For missing data occurred at visits prior to death or clinical worsening event, missing data will be imputed by the LOCF approach.
- For all other withdrawals, the LOCF approach will be used for imputation.

For missing Borg dyspnea score at visits beyond Week 48, the missing data will not be imputed, and all analyses will be based on the observed case.

WHO FC:

- For those subjects who withdrew early due to death or have no WHO FC due to a clinical worsening event, the WHO FC is set to the worst value of class IV.
- For missing data occurred at visits prior to death or clinical worsening event, missing data will be imputed by the LOCF approach.
- For all other withdrawals, the LOCF approach will be used for imputation.

For missing WHO FC at visits beyond Week 48, the missing data will not be imputed, and all analyses will be based on the observed case.

NT-proBNP:

- For NT-proBNP, the missing value at visits up to Week 36 will be imputed using the LOCF approach.
- Subjects with missing Baseline NT-proBNP values, the Baseline measure will not be imputed, and these subjects will be excluded from the analyses of the NT-proBNP.

- Subjects with NT-proBNP values reported below the lower limit of quantification, half of the lower limit of quantification will be used for summary and analysis. For example, if the result is reported as '<2.4 pmol/L', a numeric value of  $2.4/2=1.2$  pmol/L will be used.

The missing values at visits beyond Week 36 will not be imputed and all analyses will be based on the observed cases.

Hemodynamics:

Missing values for hemodynamic parameters will not be imputed. The summary and analyses will be based on the observed cases.

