#### **8.4 MULTIPLE COMPARISONS AND MULTIPLICITY**

Experimental wise Type I error rate will be controlled at no greater than 0.05 (for 2-sided hypotheses). The study will include an interim analysis for efficacy when 75% of the pre-specified total adjudicated events have occurred. The primary efficacy endpoint will be tested at an interim analysis with an alpha level of 0.020 (2-sided) and at the final analysis at an alpha of 0.044 (2-sided) with the overall Type I error rate controlled at 0.05. Efficacy boundaries for early stopping of the study are calculated based on the O'Brien-Fleming alpha-spending function.

The effect of treatment will be formally tested on the following 3 key secondary efficacy endpoints:

- Change from Baseline in 6MWD at Week 24
- Change from Baseline in NT-proBNP at Week 24
- Change from Baseline in combined 6MWD/Borg dyspnea score at Week 24

In order to control the Type I error rate, the hierarchical (fixed-sequence) test procedure will be used. The p-value for the change from Baseline in 6MWD at Week 24 will be tested at a 2-sided Type I error rate of 0.05. The subsequent tests for change from Baseline in NT-proBNP at Week 24 and then the change from Baseline in combined 6MWD/Borg dyspnea score at Week 24 will be tested only if the preceding test is statistically significant.

The statistical tests for other secondary endpoints below are considered exploratory and no multiplicity adjustment will be applied. For data collected beyond the specified week (eg, Week 48 for 6MWD, Borg score, WHO FC; Week 24 for RHC hemodynamics; and Week 36 for NT-proBNP), descriptive summaries will be provided with no statistical testing.

- 6MWD at all time points prior to Week 48 (other than Week 24)
- Borg dyspnea score at visits prior to Week 48
- WHO FC at visits prior to Week 48
- RHC hemodynamics at Week 24
- NT-proBNP at all time points prior to Week 36 (other than Week 24)

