### **10.3.4 NT-proBNP**

NT-proBNP at weeks 12 and 36 will be analysed in the same way as described in Section 10.2.2. In addition, NT-proBNP at weeks 12, 24, and 36 will also be analysed with LOCF imputation for missing data. NT-proBNP at other timepoints will only be summarized.

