14.2.2.7	Summary and Analysis of 6MWD (meter) at Week 24 with No Imputation for Missing Data
14.2.2.8	Summary and Analysis of 6MWD (meter) at Week 24 Including Data Collected After Termination of Study Drug
14.2.2.9	Summary and Analysis of 6MWD (meter) at Week 24 by Etiology
14.2.2.10	Summary and Analysis of 6MWD (meter) at Week 24 by Baseline WHO Functional Class
14.2.2.11	Summary and Analysis of 6MWD (meter) at Week 24 by Geographic Region
14.2.2.12	Summary and Analysis of 6MWD (meter) at Week 24 by Sex
14.2.2.13	Summary and Analysis of 6MWD (meter) at Week 24 by Age Group
14.2.2.14	Summary and Analysis of 6MWD (meter) at Week 24 by Study Drug Dose
14.2.2.15	Summary and Analysis of 6MWD (meter) at Week 24 by UT-15C Dose Quartile at Week 24
14.2.2.16	Summary and Analysis of 6MWD (meter) at Week 24 by Background PAH Therapy
14.2.2.17	Summary and Analysis of 6MWD (meter) at Week 24 by Baseline 6MWD Category
14.2.2.18	Summary and Analysis of 6MWD (meter) at Weeks 4, 8, 12, 36, and 48
14.2.2.19	Summary of 6MWD (meter) by Visit with Observed Case
14.2.3.1	Summary and Analysis of NT-proBNP (pg/mL) Data at Week 24
14.2.3.2	Summary and Analysis of NT-proBNP (pg/mL) Data at Weeks 12 and 36

Table Number	Table Title
14.2.3.3	Summary and Analysis of NT-proBNP (pg/mL) Data at Weeks 12, 24, and 36 with LOCF Imputation
14.2.3.4	Summary of NT-proBNP (pg/mL) Data by Visit
14.2.3.5	Analysis of NT-proBNP (pg/mL) at Week 24 Using Mixed Model Repeated Measurement (MMRM) – ITT Population
14.2.3.6	Analysis of NT-proBNP (pg/mL) at Week 36 Using Mixed Model Repeated Measurement (MMRM) – ITT Population
14.2.4.1	Summary and Analysis of Borg Dyspnea Score up to Week 48
14.2.4.2	Summary of Borg Dyspnea Score by Visit with Observed Case
14.2.5.1	Summary and Analysis of WHO Functional Class up to Week 48
14.2.5.2	Summary of WHO Functional Class by Visit with Observed Case
14.2.6	Summary and Analysis of Hemodynamic Parameters at Week 24
14.2.7	Summary of Hospitalization Information
14.3.1.1	Overall Summary of Adverse Events
14.3.1.2	Summary of Adverse Events by System Organ Class and Preferred Term
14.3.1.3	Summary of Adverse Events by System Organ Class
14.3.1.4	Summary of Adverse Events by Preferred Term
14.3.1.5	Summary of Deaths
14.3.1.6	Summary of Serious Adverse Events by Preferred Term
14.3.1.7	Summary of Adverse Events Probably or Possibly Related to Study Drug by Preferred Term

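### The formal Week 24 NT-proBNP test is an observed-case ANCOVA that drops subjects who worsen before the window opens, unequally by arm, and SAP 8.3 and 8.3.3 are not aligned with it

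*SAP*

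**What the plan says.** - **Role of the test.** SAP 8.4 orders the key secondary tests as 6MWD, NT-proBNP, then combined 6MWD/Borg, all at Week 24. Each later one "will be tested only if the preceding test is statistically significant".
- **Formal analysis.** SAP 10.2.2 compares the change in log NT-proBNP by ANCOVA on treatment and baseline log value. "Subjects who do not have a valid NT-proBNP measurement at Baseline or Week 24 will be excluded from the analysis".
- **LOCF and MMRM in the same section.** "Additional analyses will also be performed for the data with imputation", using LOCF at Week 24. Then: "A longitudinal data analysis using MMRM will also be performed to estimate the treatment difference". The MMRM has its own table, 14.2.3.5.
- **Other endpoint-specific text.** SAP 10.3.4: "NT-proBNP at weeks 12, 24, and 36 will also be analysed with LOCF imputation for missing data". The table list keeps "Summary and Analysis of NT-proBNP (pg/mL) Data at Weeks 12, 24, and 36 with LOCF Imputation" (14.2.3.3) apart from the Week 24 analysis (14.2.3.1).
- **General missing-data text.** SAP 8.3: "For 6MWD and other key secondary efficacy endpoints, missing data will be imputed as described in the sections below". SAP 8.3.3: "For NT-proBNP, the missing value at visits up to Week 36 will be imputed using the LOCF approach". Neither sentence says whether this is the main or a supportive analysis.
- **Windows.** In SAP Table 8-1 the NT-proBNP Week 12 window ends on Day 127 and the Week 24 window covers Days 128 to 211. SAP 8.6.2 keeps one observation per window, the one closest to the target day.
- **Sampling.** Protocol 3.2.1.5 takes NT-proBNP at the Study Drug Termination visit, and protocol 7.4 places that visit before down-titration.

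**The concern.** A subject whose clinical worsening ends participation before the Week 24 window opens has no Week 24 value and leaves the formal comparison. Worsening is the primary outcome and is expected more often on placebo. The subjects left are therefore selected by a post-randomisation outcome that treatment is assumed to change, and the arms are no longer protected by randomisation. If worsening goes with rising NT-proBNP, more of the high values are removed from placebo, which pulls the arms together.

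Week 12 values, and termination samples taken by Day 127, exist for many of these subjects but play no part in the formal test. The test also gates a third formal endpoint. The unqualified imputation sentences in 8.3 and 8.3.3 leave the SAP without one clear statement of the missing-data rule for it.

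**Working it through.** **1. The plan's own figures.** Protocol 10.2 and SAP 5 assume exponential times, a placebo median of 32 months and a hazard ratio of 0.62.
- Placebo hazard: ln 2 / 32 = 0.02166 per month. UT-15C hazard: 0.62 × 0.02166 = 0.01343.
- Month 12: 1 − exp(−0.02166 × 12) = 22.9% and 1 − exp(−0.01343 × 12) = 14.9%. The plan states 23% and 15%.
- Power of the primary with 205 events: Φ(√205/2 × |ln 0.62| − 1.960) = Φ(1.462) = 92.8%, consistent with the stated 90% or more.

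The inputs reproduce. No corresponding figure is given for NT-proBNP.

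**2. Who has worsened before the window opens.** Day 127 = 127/30.44 = 4.17 months.
- Placebo: 1 − exp(−0.02166 × 4.17) = 8.6%, about 26 of 305.
- UT-15C: 1 − exp(−0.01343 × 4.17) = 5.4%, about 17 of 305.

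By Day 168 the figures are 11.3% and 7.1%, but a termination sample taken on Days 128 to 211 counts as Week 24, so some of these later subjects stay in. Discontinuation for other reasons comes on top.

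**3. What the MMRM can recover.** A subject who stops before the Week 12 sample can enter the MMRM with the termination value as the Week 12 record. A subject sampled at Week 12 (target Day 85) who stops on Days 86 to 127 normally keeps the Week 12 value, and 8.6.2 discards the termination sample. On placebo, 5.9% have worsened by Day 85, so this concerns (8.6 − 5.9)/8.6, about 32% of events by Day 127 using unrounded figures. The MMRM therefore uses some post-baseline data from most dropped subjects, but not every early termination sample. A death without any sample adds nothing.

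**4. Loss against complete data.** With missing share m, power ≈ Φ(√(1 − m) × (1.960 + z) − 1.960), where z is 1.282 for 90% and 0.842 for 80% power with complete data.
- From an assumed 90%: 86.8%, 84.8% and 82.6% at m = 10%, 15% and 20%.
- From an assumed 80%: 75.7%, 73.3% and 70.7%.

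Complete data are not attainable, so the useful comparison is between the analyses already in the SAP.

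**5. Simulated power, N = 610, two-sided 0.05.** Every NT-proBNP input (effect, SD, correlation, loss, log rise at worsening) is an assumption.

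| Assumptions | Observed cases | MMRM | LOCF |
|---|---|---|---|
| A: effect −0.15, 5% other loss per arm, rise 0.3 | 69.5% | 77.0% | 81.9% |
| A, rise 0.7 | 70.2% | 79.2% | 84.0% |
| A, rise 1.1 | 70.8% | 80.9% | 84.9% |
| B: effect −0.15, SD 0.65, correlation 0.7, other loss 5% placebo and 15% active, 8.6.2 applied, rise 0.3 | 73.6% | 74.0% | 79% |
| B, rise 0.7 | 73.3% | 77.8% | 84% |
| C: effect −0.20, SD 0.8, correlation 0.7, 15%/15% missing at random | 80.4% | not run | 82.3% |
| C, 15%/22% (placebo/active) missing at random | 79.9% | not run | 79.2% |
| C, 12%/20%, worsened subjects missing | 66.3% | not run | 65.6% |

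MMRM minus observed cases: 7.5, 9.0 and 10.1 points in A; 0.4 and 4.5 in B. A further set (20% of events being deaths without a sample, 8.6.2 applied, SD 0.65 or 0.8) gave 4 to 9. LOCF in set C carries only a baseline or Week 12 value, never a termination sample.

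**6. Bias.** In the last C row a true −0.20 is estimated as −0.158 by observed cases and −0.143 by LOCF. With no true effect and the same missingness, the estimates are +0.041 and +0.028, against UT-15C, and rejection is 12.0% and 9.3%, against 6.2% with complete data. LOCF does not remove the selection.

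**The case against.** The strongest reply is that the SAP already settles which analysis leads. SAP 10.2.2, SAP 10.3.4 and the separate tables all make LOCF additional, and the opening of 8.3.3 names Borg and WHO functional class, not NT-proBNP, when it speaks of main analyses. SAP 8.3 is just as loose about 6MWD, whose Week 24 MMRM in 10.2.1 uses observed measures. On this view Section 8 says how to impute and Section 10 says where. This largely stands. A reader might infer that the p-value depends on which section is followed; the documents do not support that as a live choice. What remains is unqualified wording that should be aligned.

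Three further replies also stand:
- A reader might infer that everyone who died or worsened is dropped, or that termination samples go unused. Samples on Days 128 to 211 enter the ANCOVA, and earlier ones feed the planned LOCF analysis.
- A reader might infer that 6MWD is treated better because it gets a worst score. SAP 8.3.2 applies that score only in the covariance analyses, not in the 6MWD MMRM, and an NT-proBNP MMRM would give none either.
- The choice of lead analysis is partly a preference. The MMRM assumes missing at random, which is doubtful after death.

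None of this answers the selection in step 2, which follows from 10.2.2 read exactly as intended.

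**Conclusion.** The point holds in a limited form. The formal Week 24 NT-proBNP test conditions on an outcome expected in about 8.6% of placebo and 5.4% of UT-15C subjects before the window opens. It discards their earlier on-treatment values, and two general passages in the SAP do not match it. The percentages rest on the plan's exponential hazards and assume that a subject who worsens by Day 127 has no later in-window sample.

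A reader might go further and infer a definite loss of power. The documents do not support a figure, because they give no NT-proBNP effect, SD, correlation or dropout by arm at Week 24. Under the inputs tried, the MMRM gained roughly 0 to 10 points over observed cases and was never less powerful. LOCF ranged from clearly better to slightly worse, depending on whether it carried termination samples and on how loss differed by arm.

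The primary endpoint is unaffected. This should be fixed before unblinding, as an improvement to one key secondary test and the test that it gates.

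**What to change.** - In SAP 10.2.2, name the MMRM already specified there (change in log NT-proBNP; treatment, week and their interaction; baseline log value) as the single formal Week 24 test. SAP 10.2.1 likewise lists an MMRM first for 6MWD. Label the observed-case and LOCF ANCOVAs supportive.
- Reword the sentence in 8.3 and the NT-proBNP bullet in 8.3.3 so that LOCF applies only to the supportive analysis.
- Do not state that the MMRM uses all early termination samples, because 8.6.2 keeps only the observation closest to the target day.
- Add a supportive worst-rank analysis for death and clinical worsening, because the MMRM gives these subjects no worst score.

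The cost is SAP wording and one added supportive analysis; the MMRM table (14.2.3.5) is already planned and no new data are needed. The downside is reliance on missing at random for the formal test, which the supportive analyses help to check.
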